The primary purposes of this study are to establish feasibility and acceptability of the UZIT intervention. A descriptive analysis will be applied. Pilot feasibility and acceptability studies of integrative behavioral approaches similar to the one proposed here generally include 6-19 participants (Cohen et al., 2007; Freedenberg, Thomas, & Friedmann, 2015; Lengacher et al., 2011; Palumbo, Wu, Shaner-McRae, Rambur, & McIntosh, 2012; Uebelacker et al., 2010; Yeh et al., 2010). With regards to preliminary efficacy outcomes of PH-related symptoms and PH-related HRQoL, we estimated statistical power. Power analysis using two-sided paired tests (*t*-tests for continuous and McNemar test for dichotomous/categorical outcomes) indicates that a sample size of 15 has sufficient power (≥ 0.8) to detect large effect size (standardized mean difference of 0.78 or greater for continuous outcomes; odds ratio of 7 or greater for dichotomous/categorical outcomes, assuming that proportion of discordant pairs is 0.6) with a significance level of 0.05. Therefore, small to medium effect sizes will not be detected as statistically significant in this study. As a pilot study to generate information on preliminary efficacy, we will not rely on statistical significance, but rather on clinical differences. Anticipating 10-15% attrition rate over a 6-8 week behavioral intervention study (Carter et al., 2013; Grossman et al., 2010), we will enroll 20 participants to achieve a final minimum sample of 15.

C. Measurement / Instrumentation

Table 1 outlines the data collection timeline. Participants will provide demographic data at enrollment. The PI's preliminary work demonstrated that PH patients were able to complete four questionnaires in outpatient clinic settings within 15-minutes without undue burden. One hundred and eleven participants of 115 enrolled (96.5%) completed all four questionnaires without difficulty.

Table 1: Data Collection Timeline

Measurement	Study AIMS	Week 0	Week 1	Week 2	Week 3	Week 4	Week 5	Week 6
Consent		X						
Demographics		X						
UZIT Intervention			X	X	X	X	X	X
Phone Call			X	X	X	X	X	X
Diary Record	2, 3b		X	X	X	X	X	X
Field Notes	2		X	X	X	X	X	X
Debriefing (P)	2				X			X
Debriefing (I)	2, F		X	X		X	X	
Session Video Recording	2, F		X	X	X	X	X	X
Acceptability Survey	2							X
PAHSS	3b		X					X
Dyspnea, Pain, Fatigue, Anxiety	3a		X	X	X	X	X	X
Manipulation Check	F						X	
Enactment Check	F						X	
CAMPHOR	3b		X					X

Data Collection Instruments

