Aim 3A: To explore the preliminary efficacy of weekly UZIT sessions on dyspnea, pain, fatigue, and anxiety. Symptoms of dyspnea, pain, fatigue, and anxiety (symptom intensity) will be assessed in response to each UZIT session. We will plot the weekly visit rating of symptoms (dyspnea, pain, fatigue and anxiety) trajectory pattern from week 1 through week 6 for each participant and by biological variables (e.g. age groups, sex, and NYHA classification). Mixed effect modeling for repeated measures will be used to model the change over time. Estimates derived from mixed effect modeling will be more accurate by accounting for within-subject correlation. It also has the advantage of the most efficient use of data. Estimates are derived from all available data, not just data from completers.

Aim 3B: To explore the preliminary efficacy of 6-week UZIT program on PH-related symptoms and HRQoL. We will compare pre-and post-differences in composite symptoms' presence and severity (PAHSS) and HRQoL (CAMPHOR domains) using McNemar tests for paired proportions and dependent *t*-tests for paired means. As a pilot study to generate information on preliminary efficacy, we will rely on clinical differences. The point estimates and effect sizes from this pilot study will guide the sample size calculation for future larger scale study (efficacy and effectiveness). We will primarily report summary statistics on proportions and 95% confidence intervals at each time point. We will also determine the correlation between changes in PAHSS and CAMPHOR scores with a dose of home practice (minutes/week) to indicate a dose-effect relationship. Furthermore, the frequency and the amount of home practice can serve as an indicator of participants' acceptability of the UZIT program.

IV. Bibliography

Include a reference list of literature cited to support the protocol statement.

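### Aim 3B estimates change from completers only, unlike Aim 3A; the likely bias is small, its mechanism is assumed, and a two-visit mixed model plus Week 6 follow-up would deal with most of it cheaply

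*Combined protocol and SAP*

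**What the plan says.** In E. Data Analysis, Aim 3A (weekly dyspnea, pain, fatigue and anxiety) gets a repeated-measures model: "Mixed effect modeling for repeated measures will be used to model the change over time". One reason given is "Estimates are derived from all available data, not just data from completers".

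The next paragraph, Aim 3B, analyses pre-post change in PAHSS and CAMPHOR with McNemar tests for the proportions and "dependent *t*-tests for paired means". It then states a use for the results: "The point estimates and effect sizes from this pilot study will guide the sample size calculation for future larger scale study".

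Table 1 (C. Measurement / Instrumentation) schedules PAHSS and CAMPHOR at Week 1 and Week 6 only.

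On expected loss, Sample Size and Statistical Power anticipates 10-15% attrition and enrols 20 to finish with at least 15. Aim 1 sets a retention target of at least 70%.

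For Aim 3B the plan gives no missing-data method, no comparison of completers with dropouts and no sensitivity analysis.

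**The concern.** A paired test on two visits needs both forms. A participant who gives Week 1 scores and then leaves contributes nothing, so Aim 3B is a completer analysis in effect, although the plan does not call it one. The plan gives no reason for using all available data in one sub-aim and not in the other.

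The plan says it will rely on estimates rather than significance, and it wants those estimates for planning. Bias in the estimated change therefore matters more here than power. If those who leave differ at Week 1 from those who stay, the effect size carried forward describes a selected group.

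**Working it through.** **1. The plan's own figure.** Two-sided paired t-test, 15 pairs, standardized change 0.78, alpha 0.05. The noncentrality is 0.78 × √15 = 3.02 on 14 degrees of freedom, and the power is 0.802. The statement that "a sample size of 15 has sufficient power (≥ 0.8) to detect large effect size", with "standardized mean difference of 0.78 or greater for continuous outcomes", reproduces for the t-test.

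**2. How many pairs are lost.** From 20 enrolled:
- 10-15% attrition loses 2-3 people and leaves 17-18 pairs.
- 15 of 20 is a 25% loss.
- 70% retention leaves 14 pairs.

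**3. Size of the bias if dropout depends on baseline.** The documents do not give what is needed here, so I assume:
- Week 1 and Week 6 scores are normal with equal SD, and higher is worse.
- The pre-post correlation ρ is 0.4 to 0.8.
- The odds of dropout are multiplied by 2 or 3 per SD of worse baseline.

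Let m be how far, in SD of the score, the completers' mean baseline lies below that of all starters. It follows numerically from the logistic dropout model. Change regresses on baseline with slope ρ − 1, so the completer mean change is shifted towards less improvement by

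bias = (1 − ρ) × m.

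| Dropout | Odds ratio per SD | m | Bias at ρ = 0.8 | Bias at ρ = 0.4 |
|---|---|---|---|---|
| 10% | 2 | 0.066 | 0.013 | 0.040 |
| 10% | 3 | 0.098 | 0.020 | 0.059 |
| 15% | 2 | 0.098 | 0.020 | 0.059 |
| 15% | 3 | 0.142 | 0.028 | 0.085 |
| 25% | 2 | 0.159 | 0.032 | 0.096 |
| 25% | 3 | 0.228 | 0.046 | 0.137 |

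Simulation of 20 enrolled agrees to within about 0.01: 0.01-0.08 SD at 12.5-15% dropout and 0.03-0.13 SD at 25%.

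**4. What a likelihood-based model does.** With two visits it estimates the Week 6 mean as the completers' mean plus b × (baseline mean of all − baseline mean of completers), where b is the completers' slope of Week 6 on Week 1. It then subtracts the baseline mean of all. Simulated bias was at most 0.005 SD.
- Precision is nearly unchanged: at 25% dropout and ρ = 0.4 the sampling SD is 0.28 for both estimators.
- Root-mean-square error at 15% dropout and ρ = 0.4 is 0.266-0.274 for completers and 0.257-0.263 for likelihood.
- At 25% dropout and ρ = 0.8 it is 0.167-0.170 and 0.168-0.172, so there is no gain.

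**5. Other dropout mechanisms.** The true change is assumed to be 0.78 SD of the change, with 15-30% dropout and ρ of 0.5 or 0.7.

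| Dropout depends on | Completers | Likelihood |
|---|---|---|
| Nothing (random) | about 0.78 | about 0.78 |
| Worse baseline | 0.63-0.72 | 0.77-0.78 |
| Less improvement | 0.92-1.07 | 0.89-1.02 |

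**6. Planning consequence, for scale only.** Suppose the paired effect size were carried straight into a two-arm trial at 80% power. Then n per arm = 2 × (1.96 + 0.842)² / d² ≈ 15.7 / d²:
- d = 0.78 gives 26.
- d = 0.712 (15% dropout, ρ = 0.5) gives 31.
- d = 0.63 (30% dropout, ρ = 0.5) gives 40.

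**7. By-visit summaries.** The plan also reports summaries at each time point. If the Week 1 mean uses everyone and the Week 6 mean only completers, their difference is biased the other way by ρ × m. At 25% dropout that is 0.4 × 0.159 = 0.06 to 0.8 × 0.228 = 0.18 SD. The summaries do not repair the paired estimate.

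**The case against.** The strongest reply is that this is a conventional analysis for an exploratory, secondary aim in a 20-person feasibility study that says it will not rely on significance. Near the planned attrition the bias is well below the sampling SD of 0.15-0.26. Aim 3A has six visits, so its model uses partial trajectories, whereas here a model adds only the dropouts' Week 1 scores. In an uncontrolled pre-post study, natural change and regression to the mean affect the planning estimate whichever estimator is used. All of this stands, and it keeps the point minor.

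A reader might infer more than the documents support:
- **That the plan expects 30% loss.** The 70% figure is a feasibility threshold. The stated expectation is 10-15%.
- **That sicker patients will leave.** The background describes a progressive, burdensome disease, which makes this plausible. But entry is limited to NYHA II/III, independent walking and willingness to complete the study. Scheduling or lack of perceived benefit could equally drive dropout.
- **That completer estimates must flatter the treatment.** If a worse baseline predicts dropout they understate improvement, so the next trial would be too large rather than underpowered. Overstatement needs dropout driven by poor response.
- **That a mixed model ends the dependence on who drops out.** Under response-driven dropout it moves 1.07 only to about 1.01.

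What remains is that the plan endorses the all-data principle, departs from it for the estimates it intends to reuse, and could apply it at almost no cost.

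**Conclusion.** The point holds as a minor improvement. Aim 3B is completer-only in effect, which is inconsistent with the plan's own reasoning for Aim 3A. If dropout depends on baseline severity, the completer mean change is off by about 0.01-0.08 SD near the planned attrition and 0.03-0.13 SD at 25% loss, in the direction of too little improvement when worse baseline predicts leaving. A likelihood-based model removes that bias with essentially no loss of precision, but the gain in total error is slight and vanishes at high correlation. These sizes rest on the assumed correlation of 0.4-0.8, the assumed odds ratio of 2-3 per SD, and normal scores with equal SDs. If dropout is random there is no bias. If it follows unseen response, changing the model helps little and only recovering the Week 6 data would.

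**What to change.** In E. Data Analysis, Aim 3B:
- **Continuous PAHSS and CAMPHOR scores:** make the main estimate a two-visit mixed model with visit as a category, unstructured covariance and everyone with at least one score. Keep the paired t-test as a sensitivity check, and state that the model estimate is the one to carry into planning.
- **Symptom presence:** keep McNemar and label it completer-only, or use a logistic mixed model if it converges at this sample size.
- **Reporting:** tabulate Week 1 scores for completers and dropouts.
- **Data collection:** ask people who stop sessions to return the Week 6 forms by mail or phone. This is the only step that addresses response-driven dropout.

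Cost: a few lines of SAP text and code, and slight extra follow-up effort. The sample size does not change.

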This study will use a single group repeated-measures design to address the following Specific Aims:

Aim #1: To determine the feasibility of a 6-week UZIT intervention in community-dwelling adults with PH. Feasibility will be determined by 1) recruitment rate (>40% recruited from those approached), 2) enrollment (\geq two participants /month) (Carter et al., 2013; Uebelacker et al., 2010), 3) home practice (\geq 1/week), and 4) retention rate (\geq 70% of participants remaining at study completion). We will also explore UZIT interventionists' perception about study feasibility.

Hypothesis 1: UZIT will meet feasibility targets for community-dwelling adults with PH.

Aim #2: To determine the acceptability of UZIT among community-dwelling adults with PH for symptom management. Acceptability will be determined by participants' evaluation of the UZIT program (composite mean System Usability Scale score > 5, scale 1-7), (Brooke, 1986) and session completion rate (at least 5 of 6 sessions [83% attendance]) (Campo et al., 2013; Cohen et al., 2007; Lee et al., 2010; Lengacher et al., 2011; Palumbo, Wu, Shaner-McRae, Rambur, & McIntosh, 2012) by the participants retained at the study end. An exploratory sub-aim (Aim 2-A) is to determine what components of the UZIT program are preferred by adults with PH. We will also explore UZIT interventionists' perception about participants' acceptability of the UZIT intervention.

Hypothesis 2: UZIT will meet acceptability standards among community-dwelling adults with PH.

Aim #3: To explore the preliminary efficacy of UZIT intervention.

Aim #3a: To explore the preliminary efficacy of weekly UZIT sessions on dyspnea, pain, fatigue and anxiety.

Aim #3b: To explore the preliminary efficacy of a 6-week UZIT program on PH-related symptoms and HrQoL.

Hypothesis 3a: Patients will report reduced presence and intensity of dyspnea, pain, fatigue and anxiety after each UZIT session.

Hypothesis 3b: Patients will report a decrease in the presence, severity, and activity interference for PH-related symptoms and improvement in HrQoL after UZIT program compared to baseline.

III. Background and Rationale

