This is an important foundational study to establish feasibility and acceptability and, potentially, to identify needed refinements, in integrative therapies for symptom management in complex chronic, life-limiting cardio-pulmonary disease. Once UZIT is established as feasible and acceptable for PH patients, future research will focus on testing the efficacy and effectiveness of UZIT to reduce symptom burden and promote HRQOL for persons with complex chronic, life-limiting cardio-pulmonary disease. Additional studies will include analysis of cost and health care utilization outcomes. The long-term goal of this program of research is to advance knowledge and evidence-based application of integrative therapies to manage symptoms and promote quality of life for persons with complex chronic, life-limiting cardiopulmonary conditions.

III. Procedures

A. Research Design

This feasibility and acceptability study will use a pre/post intervention (6-weeks UZIT program) mixed-method design with repeated (weekly) measures of a single cohort of patients with PH. We will also explore preliminary efficacy testing to construct sample size estimates for future randomized control trials. Patients will serve as their controls.

B. Sample

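### Aim 3B commits to proportions with intervals at each time point, not to an interval for the within-patient change it will interpret, and lets uncontrolled pre/post effects guide the size of a later RCT

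*Combined protocol and SAP*

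**What the plan says.** The Specific Aims (Section II) describe the design: "This study will use a single group repeated-measures design". Hypothesis 3b concerns improvement from baseline, so the quantity of interest is change within a patient. Table 1 collects PAHSS and CAMPHOR at weeks 1 and 6.

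Under Measurement, PAHSS covers both the presence of 17 symptoms and their severity on a 0 to 10 rating. CAMPHOR yields domain scores.

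The Aim 3B paragraph of Data Analysis plans a pre/post comparison "using McNemar tests for paired proportions" and dependent t-tests for means. It says clinical differences will be relied on. It then states the main output: "We will primarily report summary statistics on proportions and 95% confidence intervals at each time point". It also says: "The point estimates and effect sizes from this pilot study will guide the sample size calculation for future larger scale study".

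Research Design gives the purpose as to "explore preliminary efficacy testing to construct sample size estimates for future randomized control trials", and adds: "Patients will serve as their controls". The Sample Size and Statistical Power section says that "we will not rely on statistical significance, but rather on clinical differences" and discloses that "small to medium effect sizes will not be detected as statistically significant in this study". No size for a clinical difference on PAHSS or CAMPHOR is given anywhere.

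**The concern.** The declared primary report does not match the question in two ways.

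- **Scale.** A proportion describes symptom presence. It does not describe PAHSS severity or a CAMPHOR domain score.
- **Pairing.** An interval at week 1 and another at week 6 do not determine the interval for the change, which also depends on how each patient's two values go together. If results are read on the size of the change, its interval is the main evidence. A McNemar p value does not supply it.

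The second use raises the stakes. The effects that are to guide a randomized trial are pre/post effects in one group. They include any change that would have occurred without UZIT, and at about 15 to 18 completers they are imprecise. A report without intervals for change would leave that imprecision out of view when the next trial is sized.

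**Working it through.** **Inputs from the plan:** 20 enrolled, minimum final sample 15; 10-15% attrition (20 x 0.85 = 17, 20 x 0.90 = 18); two-sided 0.05; power at least 0.8; detectable standardized mean difference 0.78; discordant proportion 0.6. **Assumed, because the documents give no value:** pre/post correlations, equal SDs at the two visits, and the symptom counts in step 3.

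**1. The plan's own figure.** Paired t-test, n = 15, 14 degrees of freedom, noncentrality 0.78 x sqrt(15) = 3.02: power 0.802. The figure reproduces, which shows that 0.78 is in units of the SD of the change.

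**2. Scores, n = 15.** The half-width at one time point is t(0.975, 14)/sqrt(15) = 0.554 SD. The half-width for the paired change is 0.554 x sqrt(2(1 - r)) SD:

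| r (assumed) | half-width for change |
|---|---|
| 0.3 | 0.66 SD |
| 0.5 | 0.55 SD |
| 0.8 | 0.35 SD |

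The time-point intervals look the same in all three rows.

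**3. Symptom presence, n = 15, assumed 12 with the symptom before and 5 after.** The time-point report (Wilson intervals) is 80% (55 to 93) and 33% (15 to 58), whatever the pairing. The paired reduction is 7/15 = 47 points. Its Tango 95% CI is:
- 17 to 70 if 7 improve and 0 worsen (exact McNemar p = 0.016);
- 9 to 72 if 8 improve and 1 worsens (p = 0.039; discordance 9/15 = 0.6, as in the plan).

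Here the reading hardly changes. It can change more at an extreme. With 11 before and 5 after (also assumed), the 40-point reduction has Wald CI 15 to 65 with 6 improving and 0 worsening (p = 0.031), but -5 to 85 with 10 and 4 (p = 0.18).

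**4. What an observed effect implies for an RCT.** CI for the standardized change by inverting the noncentral t; RCT size from a two-sample t-test, 80% power, two-sided 0.05, treating the whole change as a between-arm effect on change scores.

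| Observed | n | 95% CI | Per arm (range) |
|---|---|---|---|
| 0.78 | 15 | 0.19 to 1.35 | 27 (10 to 445) |
| 0.78 | 17 | 0.23 to 1.32 | 27 (11 to 311) |
| 0.78 | 18 | 0.24 to 1.30 | 27 (11 to 271) |
| 0.5 | 15 | -0.05 to 1.03 | 64 (16 to no upper limit) |
| 1.0 | 15 | 0.36 to 1.61 | 17 (8 to 120) |

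The normal approximation, n = 2(1.96 + 0.84)^2/d^2, gives 26 (9 to 444) in the first row. The 80% CI there is 0.39 to 1.15, or 13 to 106 per arm. A trial of 27 per arm would have 29% power if the true effect were 0.39.

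**5. Units and attribution (normal approximation).** A change of 0.78 SD-of-change units equals 0.78 x sqrt(2(1 - r)) raw SDs: 1.10, 0.78 or 0.35 for assumed r = 0, 0.5 or 0.9. An RCT comparing post-treatment scores would then need 13, 26 or 130 per arm. If only half or a quarter of the change were due to UZIT (assumed), 26 per arm becomes 104 or 413.

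**6. What the pilot can supply.** At n = 15 the 95% limits for the SD of change are 0.73 to 1.58 times the estimate, from sqrt(14/chi-square). Sample size scales with the square of the SD, so this is a (1.577/0.732)^2 = 4.6-fold range, against 445/10 = 44.5-fold for the observed effect.

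**The case against.** The strongest reply is that this is loose reporting language in an exploratory aim. Most of that stands. A reader might infer that the change is not analysed at all. It is: paired tests are planned, and for scores the paired t-test, or a paired effect size with n, is enough to compute the interval. A reader might also infer that scores will be turned into proportions. Nothing says so: the same paragraph treats them as paired means, and proportions are right for symptom presence.

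On sizing, a reader might infer that the pilot estimate will be inserted unadjusted into the RCT calculation. The text says only that it will guide it. Nor is 10 to 445 a forecast: 0.78 is a detectable effect, not an expected one. The lack of a control arm is declared and suits a feasibility study. Only the sample size section disclaims significance; the Aim 3B paragraph says just that clinical differences will be relied on.

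What remains is that the plan does name a primary report, and that report is not the paired change. Being computable is not the same as being committed to. Disclosing low power does not supply the interval, and nothing tells the later trial's designers how to allow for an uncontrolled, imprecise estimate.

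**Conclusion.** The concern holds as a minor one. The primary Aim 3B report as worded fits one of its outcome types, symptom presence, and commits to no interval for the within-patient change. For scores at n = 15, that interval could have a half-width anywhere from 0.35 to 0.66 SD (assumed correlations 0.8 to 0.3) behind identical time-point intervals. For presence, the assumed 12-and-5 example shows a modest difference.

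Guiding RCT size from single-group effects is the more consequential part. Sampling error alone spans 10 to 445 per arm in the illustration, before any allowance for change that is not due to UZIT. This rests on treating 0.78 as if observed and as a between-arm effect. The feasibility and acceptability aims are untouched.

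**What to change.** Replace the sentence on the primary report. Make it the paired mean change with 95% CI for PAHSS severity and for each CAMPHOR domain, and the paired difference in proportions with 95% CI for symptom presence. Keep the time-point summaries as secondary and the planned tests unchanged.

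Add to the sizing statement:
- any standardized effect is given with its CI and the SD used to standardize it;
- the pilot supplies the SD of change (with CI), the pre/post correlation and retention;
- the RCT's target between-group difference is a clinically important difference stated in advance, not the uncontrolled pilot estimate.

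The cost is analysis-plan wording: no patients, visits or instruments. The clinically important difference must come from outside these documents and should be fixed before Aim 3B is analysed. The documents do not settle whether data have been seen; if they have, label the target as set afterwards. The change cannot supply a control arm, the SD of change will itself be imprecise, and the planning range will be wider and less favourable.
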